### **13.5.5 Correlation of A4 Level versus 17-OHP Level**

The Exploratory Efficacy Analysis 3.5 in [Table 1](#) is the within subject correlation of A4 Level versus 17-OHP Level. This will be assessed on the log scale by randomized treatment arm. Within a given treatment arm, the data will be organized within subject as follows: (i) dummy variable ‘vtype’= 1 for log A4 and =2 for log 17-OHP; (ii) dummy variable ‘replicate’ = 1 for

baseline, =2 for study Week 10, =3 for study Week 14 and =4 for study Week 18; and (iii) variable ‘val’ = value of log A4 or log 17-OHP. SAS code will be for the form,

```
PROC MIXED METHOD=ML DATA=X;
CLASS SUBJECT VTYPE REPLICATE;
MODEL VAL = VTYPE / SOLUTION DDFM=KR;
RANDOM VTYPE /TYPE=UN SUBJECT= SUBJECT V VCORR;
REPEATED VTYPE / TYPE=UN SUBJECT=REPLICATE (SUBJECT) ;
RUN;
```

The estimated correlation coefficient will be extracted from the VCORR matrix estimate and presented by randomized treatment arm.

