9.4.4.3 Correlation of A4 Level vs 17-OHP Level

The within subject correlation OF a4 vs 17-OHP will be assessed on the log scale by randomized treatment arm. The estimated correlation coefficient will be extracted from a variance-covariance matrix and presented by randomized treatment arm.

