To evaluate the effect of tildacerfont in reducing testicular adrenal rest tumor(s) (TART[s]) in male classic CAH subjects with TART(s) at baseline after 12 weeks on treatment	3.3.	Change in the lesion volume of TART(s) from baseline after 12 weeks on double-blind, placebo-controlled treatment (Week 18) for each treatment group
To characterize dose-exposure of Tildacerfont in CAH	3.4.	Correlation of Tildacerfont plasma concentration vs dose
To evaluate the effect of tildacerfont on biomarkers relative to each other in subjects with classic CAH over 12 weeks	3.5.	Estimate the within subject correlation of A4 and 17-OHP log scale values over time
To evaluate the effect of tildacerfont in improving quality of life (QoL) in subjects with classic CAH after 12 weeks on treatment	3.6.	Change from baseline in SF-36 total score after 12 weeks on double-blind, placebo-controlled treatment (Week 18) for each treatment group

Objective	Efficacy Analysis	
To evaluate the effect of tildacerfont in improving QoL in subjects with classic CAH	3.7.	Change from baseline at Week 76 in SF-36 total score across all ITT subjects
To evaluate the effect of tildacerfont in improving acne in classic CAH subjects with acne at baseline	3.8.	Change from baseline at Week 76 in IGA of acne severity score across all ITT subjects with acne at baseline
To evaluate the effect of tildacerfont in improving hirsutism in female classic CAH subjects with hirsutism at baseline	3.9.	Change from baseline at Week 76 in modified Ferriman Gallwey (mFG) score for hirsutism across all female ITT subjects with hirsutism at baseline
To evaluate the proportion of subjects who can reduce GC use in subjects with classic CAH	3.10.	Proportion of subjects with at least a 5 mg/day hydrocortisone equivalent (HCe) reduction from baseline in GC dose and A4 $\leq$ ULN at Week 76
To evaluate the effect of tildacerfont in reducing TART(s) in male classic CAH subjects with TART(s) at baseline	3.11.	Change in the total lesion volume of TART(s) from baseline at Week 76 across all male ITT subjects with TART(s) at baseline
To evaluate the effect of tildacerfont in reducing A4 in subjects with classic CAH over 12 weeks	3.12.	Assessment of dose response for change from baseline in log ATCH after 12 weeks on double-blind, placebo-controlled treatment (Week 18)

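### SAP 13.5.5 sets out to estimate the within-subject correlation of log A4 and log 17-OHP but reads it from VCORR, which in general does not contain that quantity

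*SAP*

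**What the plan says.** SAP Table 1, analysis 3.5, sets the task: "Estimate the within subject correlation of A4 and 17-OHP log scale values over time". SAP 13.5.5 repeats the target, saying that the analysis "is the within subject correlation of A4 Level versus 17-OHP Level". Protocol 9.4.4.3 also names a within-subject correlation, which "will be assessed on the log scale by randomized treatment arm".

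The SAP code is run within each arm on four replicates per subject: baseline and Weeks 10, 14 and 18. It has three working parts:

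- Fixed effects: "MODEL VAL = VTYPE / SOLUTION DDFM=KR". Hormone type is the only term, and there is no visit effect.
- Between-subject part: "RANDOM VTYPE /TYPE=UN SUBJECT= SUBJECT V VCORR". This is an unstructured 2×2 matrix G for subject-level A4 and 17-OHP effects.
- Within-subject part: the statement beginning "REPEATED VTYPE / TYPE=UN SUBJECT=REPLICATE (SUBJECT". This is an unstructured 2×2 matrix R for the two hormones at one visit of one subject.

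The rule for the reported figure is "The estimated correlation coefficient will be extracted from the VCORR matrix estimate". No element of that matrix is named, and no R or RCORR output is requested. The protocol is less specific: "The estimated correlation coefficient will be extracted from a variance-covariance matrix".

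**The concern.** The objective behind endpoint 3.5 is how the two hormones behave relative to each other over 12 weeks of treatment. A reader will take a within-subject coefficient as evidence on whether they rise and fall together in the same patient from visit to visit. The model isolates that information in R, but the reporting rule goes to a matrix in which G has been added back. Patients who run persistently high or low on both hormones contribute to G, and so to VCORR, whatever happens within a patient over time. The model has no covariates, so stable differences linked to sex, GC dose or severity also go into G.

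There is a second problem in the same rule. VCORR holds two different A4/17-OHP elements, one for the same visit and one for different visits. Two programmers following the text could report different numbers.

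**Working it through.** The plan states no figure for this analysis, so there is none to reproduce. The check derives what each matrix contains.

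**Inputs from the SAP.** G = (g11, g12, g22) from the RANDOM statement, R = (r11, r12, r22) from the REPEATED statement, and four replicates. Index 1 is log A4 and index 2 is log 17-OHP.

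**Inputs assumed.** The share of variance lying between subjects (ICC, taken as equal for the two hormones), the between-subject correlation ρB and the within-subject correlation ρW. The documents give none of these.

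**Formulas.** For a subject with all four visits, V is 8×8, with G in every 2×2 block and R added to the diagonal blocks. Therefore:

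- VCORR, same visit: (g12 + r12)/sqrt((g11 + r11)(g22 + r22))
- VCORR, different visits: g12/sqrt((g11 + r11)(g22 + r22))
- Within-subject, from R: r12/sqrt(r11·r22)
- Between-subject, from G: g12/sqrt(g11·g22)

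With equal ICCs the first two reduce to ICC·ρB + (1 − ICC)·ρW and ICC·ρB.

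**Numbers.** At ICC 0.7:

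- ρB 0.8, ρW 0.3: 0.7×0.8 + 0.3×0.3 = 0.56 + 0.09 = 0.65 (same visit); 0.56 (different visits).
- ρB 0.5, ρW 0.8: 0.7×0.5 + 0.3×0.8 = 0.35 + 0.24 = 0.59 (same visit); 0.35 (different visits).

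Other assumed settings:

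| ICC | ρB | ρW (value from R) | VCORR same visit | VCORR different visits |
|---|---|---|---|---|
| 0.3 | 0.8 | 0.2 | 0.38 | 0.24 |
| 0.7 | 0.8 | 0.2 | 0.62 | 0.56 |
| 0.7 | 0.8 | 0.0 | 0.56 | 0.56 |
| 0.7 | 0.2 | 0.8 | 0.38 | 0.14 |
| 0.7 | 0.8 | 0.8 | 0.80 | 0.56 |
| 0.8 | 0.8 | 0.0 | 0.64 | 0.64 |
| 0.8 | −0.3 | 0.8 | −0.08 | −0.24 |

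Across ICC 0.3 to 0.8, ρB −0.3 to 0.8 and ρW 0 to 0.8, the same-visit element minus ρW ran from −0.08 − 0.8 = −0.88 to 0.64 − 0 = +0.64. It equals ρW only in special cases, such as equal ICCs with ρB = ρW.

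**Checks.** Building V numerically at ICC 0.7, ρB 0.8, ρW 0.2 gave cross-hormone elements of 0.62 and 0.56 and none of 0.20. In simulated balanced data with the planned 18 subjects per arm, maximum-likelihood fits of this covariance model averaged 0.60 from VCORR and 0.20 from R. With ρB 0.2 and ρW 0.8 they averaged 0.39 and 0.80. The gap is therefore not a small-sample effect. With 5,000 subjects the averages were 0.62 against 0.20, and 0.38 against 0.80.

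**Time trend.** Because hormone type is the only fixed effect, any arm-level mean change between baseline and Weeks 10 to 18 stays in the residuals. If both hormones fall on average, that common fall adds positive covariance to r12 and adds variance to r11 and r22. The coefficient from R would then combine the shared mean trajectory with patient-specific tracking.

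**The case against.** The best defence is terminological. The SAP never defines the term as the correlation left after subject effects are removed, and SAP 13.3.5.1 uses similar language for the marginal covariance of repeated A4 values in an MMRM. On that usage the same-visit VCORR element is a coherent quantity, and the fault would lie only in the label. This has some force but does not settle the matter. The MMRM there concerns a single outcome. The 13.5.5 model estimates R separately for two hormones, and the endpoint is framed as over time. Even on the loose reading, the element to be reported is not named. The protocol's wording does not rescue the rule either, since an unspecified variance-covariance matrix could just as well be R.

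A second defence is that little depends on the result. Endpoint 3.5 is exploratory, SAP 10.5 gives exploratory endpoints only nominal interpretation, 13.5.5 attaches no test or threshold to the coefficient, and the code is offered as an example of form. All of that stands, and it limits the importance of the point.

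A reader might go further and infer that VCORR will overstate how closely the hormones track, because it is dominated by stable differences between patients. The documents do not support that. Dominance depends on a high ICC, which is not given, and the second worked case shows understatement.

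**Conclusion.** As written, the reporting rule does not deliver the quantity that Table 1 and 13.5.5 name. It yields either the total correlation or a between-subject covariance scaled by total variances, without saying which. That conclusion follows from the printed code and does not depend on any assumed value, apart from the special cases in which the coefficients coincide.

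The size and sign of the error cannot be known from the documents. The figures of 0.65 for a true 0.3 and 0.59 for a true 0.8 rest on an assumed equal ICC of 0.7 and on assumed correlations. They show only that the discrepancy can be material in either direction. It would also be wrong to read this as a threat to the trial's main conclusions: the A4 dose-response analysis and the secondary analyses do not use this model. This is a minor but definite correction to one exploratory endpoint.

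**What to change.** In 13.5.5, add the R and RCORR options to the REPEATED statement and report r12/sqrt(r11·r22), the same-visit A4/17-OHP element of RCORR, as the within-subject correlation for endpoint 3.5. If the G-matrix and same-visit VCORR correlations are also shown, label them between-subject and total.

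Add one sentence stating whether the arm's shared mean time trend is meant to count towards the correlation. If it is not, add VTYPE*REPLICATE to the MODEL statement so that the mean profile of each hormone is removed before R is estimated.

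The cost is small. R is already estimated by the specified model, so the first change is an output option and a sentence. The second, if wanted, is one more fixed-effect term. No new data or design change is needed. SAP 13.1 schedules endpoint 3.5 for the Week 18 primary analysis, so the choice should be recorded before that data lock.

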### **13.5.6 SF-36 Change from Baseline at Week 18 Analysis**

Exploratory Efficacy Analysis 3.6 in [Table 1](#) is the change from baseline in SF-36 for each active arm treatment group (50 mg tildacerfont QD, 100 mg tildacerfont QD, 200 mg tildacerfont QD) compared against the matching placebo group after 12 weeks of randomized, double-blinded treatment. The efficacy of tildacerfont is evaluated by comparing the change from baseline in the tildacerfont treatment group to the placebo treatment group.

#### **13.5.6.1 Statistical Modeling and Testing**

If the distribution of residuals is judged non-normal, this analysis will be accompanied by a rank-based ANCOVA model. Statistical testing will be performed using a (rank-based, if non-normal residuals) ANCOVA model. In general, the model will comprise the (rank of, if non-normal residuals) change from baseline value to study Week 18 as the dependent variable; randomized treatment group (0 = placebo, 50 = 50 mg QD tildacerfont, 100 = 100 mg QD tildacerfont, and 200 = 200 mg QD tildacerfont) and sex (0=male, 1=female) as fixed effects; baseline SF-36 total score and baseline GC dose as continuous covariates; the randomization stratum (0 =  $A4 \leq 4 \times ULN$ , 1 =  $A4 > 4 \times ULN$ ) as categorical explanatory variables. The estimation method for the ANCOVA model will REML. A significance level of 0.05 2-sided will be applied.

The ranked value is obtained by ranking all non-missing change from baseline values at the specified analysis visit, if a rank-based model is used.

### **13.5.6.2 Reporting Results**

#### **Summary of Descriptive Statistics**

Descriptive statistics (11-point) for absolute and change from baseline in SF-36 will be presented by scheduled time point (i.e., Baseline and Week 18).

#### **Presentation of Analysis Results**

The CFB least squares (LS) means will be extracted from the model for each tildacerfont dose and placebo, along with the associated SEs and 95% CIs. Further, the treatment effect for each tildacerfont dose versus placebo, being the corresponding difference in LS means, will also be extracted along with the associated SE, 95% CI and 2-sided p-values.

### **13.5.7 Change from Baseline Analyses through Week 76**

Exploratory Efficacy Analyses 3.7 to 3.11 in [Table 1](#) are the change from baseline at study Week 76 in patient- and clinician-reported outcomes (SF-36 [3.7], IGA acne score [3.8], mFG hirsutism score [3.9]); Exploratory Efficacy Analysis 3.10 is the percent of subjects with at least a 5 mg/day (HCE) reduction from baseline to study Week 76 in GC dose; and Exploratory Efficacy Analysis 3.11 is the change from baseline at study Week 76 in lesion volume of TART(s). For each of these study Week 76 exploratory endpoints, the efficacy of tildacerfont is evaluated by comparing the study Week 76 assessment against baseline.

For Exploratory Efficacy Analyses 3.7 and 3.11, an ANCOVA model will be applied, and results described, in the same manner as that for Exploratory Efficacy Analysis 3.6.

For Exploratory Efficacy Analysis 3.10, logistic regression modelling via SAS PROC GENMOD will be applied in a similar manner as for Exploratory Efficacy Analysis 3.1. The logistic regression model will include CG response (= 0 or 1) as the dependent variable; treatment group (0 = placebo, 50 = 50 mg QD tildacerfont, 100 = 100 mg QD tildacerfont, and 200 = 200 mg QD tildacerfont) and sex (0=male, 1=female as categorical covariates; log baseline A4 and baseline

GC dose (in HCe) as continuous covariates. The model will use a binomial distribution with the logit link function and a significance level of 0.05 2-sided.

The odds ratio for GC response at study Week 76 to each tildacerfont dose level versus placebo group, together with the associated 95% CI and 2-sided p-value will be extracted from the model. SAS code will be of the form,

```
PROC GENMOD DATA=x;
  CLASS SUBJECT TREATMENT VISIT;
  MODEL RESPONSE = TREATMENT VISIT / DIST=BINOMIAL LINK=LOGIT TYPE3
    AGGREGATE=TREATMENT;
  LSMESTIMATE TREATMENT 'OR 50MG V PCBO' -1 1 0 0 / EXP CL ALPHA=0.05;
  LSMESTIMATE TREATMENT 'OR 100MG V PCBO' -1 0 1 0 / EXP CL ALPHA=0.05;
  LSMESTIMATE TREATMENT 'OR 200MG V PCBO' -1 0 0 1 / EXP CL ALPHA=0.05;
  RUN;
```

Since Exploratory Efficacy Analyses 3.8 and 3.9 relate to ordinal, logistic regression modelling via SAS PROC GENMOD will be applied as described in [Section 13.5.1.2](#).

Since the change from baseline in IGA or mFG may have sparse values may have sparse values (i.e., < 5 distinctive values with counts  $\geq 5$ ), the change from baseline values will be further classified in fewer ordered categories (i.e., improvement, no change, worsening) prior to analysis.

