9.4.4 Analysis of the Exploratory Efficacy Endpoints

9.4.4.1 Testicular Adrenal Rest Tumor Endpoints

The exploratory endpoint, change in TART lesion volume at Week 18, will be analyzed using an ANCOVA model with baseline lesion size as a covariate and fixed effects for randomization strata and treatment. Additional covariates may be specified in the SAP.

The exploratory endpoint, change in TART lesion volume at Week 76, will be analyzed using a repeated measure mixed effects model with treatment and visit as fixed effects, subject as a random effect, and the baseline score as a covariate. Additional covariates may be specified in the SAP.

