9.4.4.4 Patient- and Clinician-Reported Outcomes Endpoints

Changes in SF-36 total score, IGA acne score, and mFG hirsutism score will be analyzed using a repeated measure mixed effects model with treatment (two covariates: randomized and group at Week 76) and visit as fixed effects, subject as a random effect, and the baseline score as a covariate if >2 timepoints are assessed. If only the baseline timepoint and a single post-baseline timepoint are assessed for the endpoint, an ANCOVA model with the baseline score as a covariate will be used with only a single treatment covariate (randomized treatment). There will be no imputation of missing data.

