### **5.2.5.3 Quality of Life Assessments: Short Form 36**

Quality of life will be measured using the SF-36, which will be administered on Day 1 of the Run-in Period; Week 6 (baseline), Week 18, and Week 76 of the Treatment Period, as shown in [Table 14](#).

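### SAP 13.5.7 replaces the protocol's repeated-measures model for Week 76 SF-36 and TART volume with a single-visit ANCOVA, does not declare the change, and so leaves out Week 18 data from subjects with no Week 76 value (minor; exploratory endpoints)

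*SAP*

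**What the plan says.** **Protocol.** Section 9.4.4.1 is unconditional for TART: "The exploratory endpoint, change in TART lesion volume at Week 76, will be analyzed using a repeated measure mixed effects model with treatment and visit". Both of these terms are fixed, subjects enter as random, and the model adjusts for baseline. Section 9.4.4.4 gives the same type of model for SF-36 ("Changes in SF-36 total score, IGA acne score, and mFG hirsutism score will be analyzed using a repeated measure mixed effects model with treatment"; visit is again a fixed term) when more than two timepoints are assessed. It allows a baseline-adjusted ANCOVA in one case: "If only the baseline timepoint and a single post-baseline timepoint are assessed for the endpoint, an ANCOVA model with the baseline score". The same section rules out imputation. The synopsis states the same rule and the same ban on imputation for the quality-of-life and TART endpoints together.

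**Schedule.** SAP 5.2.5.3 places SF-36 at Day 1 of the run-in and then at "Week 6 (baseline), Week 18, and Week 76 of the Treatment Period". SAP 5.2.5.2 follows men with TART at baseline at Weeks 18 and 76.

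**SAP analysis.** Section 13.5.7 states "For Exploratory Efficacy Analyses 3.7 and 3.11, an ANCOVA model will be applied, and results described, in the same manner as that" set out for analysis 3.6. That model (SAP 13.5.6.1) has change to a single visit as its dependent variable, with no visit term and no subject effect. SAP 10.2.1 provides imputation for A4 only.

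**Endpoint definition.** SAP Table 1 defines 3.7 as "Change from baseline at Week 76 in SF-36 total score across all ITT subjects". It defines 3.11 over all male ITT subjects who had TART at baseline.

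**Declared changes.** SAP Section 4 says departures from the protocol's analyses are described in Section 15. Section 15 reports one change of model, to a cumulative logit for IGA and mFG. It does not mention SF-36 or TART.

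**The concern.** The protocol's own test for using ANCOVA (one post-baseline timepoint) is not met, yet the SAP uses ANCOVA. Section 15 deals with the protocol's rule for IGA and mFG and is silent on SF-36, so a reader would take the SF-36 and TART models to be unchanged. SAP Section 4 gives the SAP precedence, so the undeclared ANCOVA is what will be run.

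The consequence concerns who is counted. The ANCOVA uses only subjects with a Week 76 value, although the endpoints are defined over ITT subjects. All subjects are on active drug from Week 18 and on one dose from Week 30, and Protocol 9.4.1 limits Week 76 analyses to change from baseline. There is therefore no concurrent arm in which selective retention might partly cancel. If subjects doing poorly at Week 18 leave more often, the Week 76 improvement is overstated, and the Week 18 data that could correct for this are set aside.

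**Working it through.** **1. Which branch of the protocol rule applies.**

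| Endpoint | Visits | Post-baseline visits | Protocol model | SAP model |
|---|---|---|---|---|
| SF-36 (3.7) | Week 6 baseline, Week 18, Week 76 | 2 | Repeated measures | Single-visit ANCOVA |
| TART volume (3.11) | Baseline (up to Week 4), Week 18, Week 76 | 2 | Repeated measures | Single-visit ANCOVA |

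Both endpoints have two post-baseline visits, so the ANCOVA branch is not available under the protocol.

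**2. The plan's own figure.** Protocol 9.2 takes 15 per group and 15% dropout: 15 / (1 − 0.15) = 17.6, rounded up to 18; 18 × 4 = 72. This reproduces.

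**3. Subjects used for SF-36 at Week 76.** With 15% lacking a Week 76 value:
- ANCOVA: 72 × 0.85 = 61.2, so about 61 used and 72 × 0.15 = 10.8, about 11, excluded.
- Repeated measures: 61.2 + 10.8 × p, where p is the share of the excluded subjects who have a Week 18 value. The documents do not give p. The result is 61 for p = 0, 67 for p = 0.5 and 72 for p = 1.
- At other dropout rates the ANCOVA uses 68 (5%) or 54 (25%).

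The number of men with TART at baseline is not given, so there is no corresponding TART count.

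**4. Size of the bias, under assumed inputs.** The documents give no SD, correlation or dropout mechanism for SF-36. Assume n = 72, SD of change 12 points, correlation 0.6 between Week 18 and Week 76 change, and dropout odds 1.6 to 2.7 times higher per SD worse at Week 18. The quantity examined is the raw mean change among subjects with Week 76 data, not the full ANCOVA.

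Bias = correlation × SD × (mean standardised Week 18 change among those retained) = 0.6 × 12 × m = 7.2 m.

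- Simulation at 15% dropout gives a bias of about 0.5 to 1.0 points, that is, m of about 0.07 to 0.14 (0.5 / 7.2 and 1.0 / 7.2).
- SE of the completers' mean: 12 / √61.2 = 1.53. Ratios: 0.5 / 1.53 = 0.33 and 1.0 / 1.53 = 0.65.
- At 25% dropout the bias is about 0.85 to 1.5 points.
- With correlation 0.3 the factor is 3.6 in place of 7.2, so the 15% figures halve to about 0.25 to 0.5.
- If dropout is unrelated to response, the bias is zero.

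A likelihood estimate that uses Week 18 with unstructured covariance has bias of about zero when every dropout was seen at Week 18, and its SE is no larger.

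**5. A second illustration in SD units.** Assume a true mean change of 0.50 SD, 15% dropout, correlations between visits of 0.4 to 0.7, and log-odds of dropout rising by 1 to 2 per SD of poorer Week 18 change. Completers' means are 0.54 to 0.63, while the repeated-measures estimate stays at about 0.50. If dropout depends only on the Week 18 level and the correlations between visits are equal, neither estimate is biased.

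**The case against.** **The change is permitted.** Protocol 9.4.1 allows changes fixed in the SAP before database lock, and SAP Section 4 makes the SAP govern. This stands: a reader might infer that the ANCOVA breaches the protocol, and it does not. What was not followed is the SAP's own undertaking to list changes in Section 15.

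**Dropouts are not simply removed.** A reader might infer that everyone who stops treatment is lost. Protocol 7.1 asks sites to keep collecting scheduled data after drug discontinuation where possible, and the SAP's Week 76 window runs from Day 513 to Day 575. Anyone measured in that window stays in the ANCOVA. Week 18 values are also analysed in their own right in 3.3 and 3.6. Only subjects with no Week 76 value are affected.

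**Eleven is a ceiling.** The 15% covers the whole Treatment Period, including the 12 weeks before Week 18. Subjects lost before Week 18 contribute to neither model, so the recoverable number is 0 to 11.

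**The bias figures are illustrative.** The inputs are assumed, the estimator is a raw mean, and every bias at 15% dropout is below one SE. If half the dropouts leave before Week 18 at random, the completers' bias falls to about 0.3 to 0.6 points. This stands.

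**The protocol's literal model is not a full remedy.** A reader might infer that restoring it removes the bias. It does so only under missing at random, with an adequate covariance structure, and for subjects seen at Week 18. If half the dropouts leave before Week 18 for reasons related to response, the unstructured estimate keeps a bias of roughly 0.2 to 0.6 points over 15% to 25% dropout. A random-intercept form with unequal variances (SD 8 at Week 18, 12 at Week 76) kept 0.23 to 0.38 points. The protocol also lists no treatment-by-visit term, although Week 18 spans placebo to 200 mg and Week 76 is all 200 mg; a single-visit ANCOVA avoids that constraint. These limits shape the fix but do not justify discarding Week 18.

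**An imputation rule might seem to cover this.** Protocol 9.4.1 has a general retrieved-dropout statement, but the synopsis and 9.4.4.4 exclude imputation for these endpoints, and SAP 10.2.1 confines it to A4.

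**Conclusion.** The departure from the protocol's model is established by the text, as is its absence from Section 15. It is more than a missing line, because the governing analysis excludes subjects whose Week 18 data are scheduled for collection, for endpoints defined over ITT subjects and reported without a control.

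For SF-36 the loss is at most about 11 of 72 at the planned dropout. The likely distortion at that rate is a fraction of one standard error, and only if dropout is related to Week 18 response. Nothing numerical can be said for TART. Both endpoints are exploratory and outside alpha control (SAP 10.5), so the primary and secondary conclusions are untouched. Severity is minor.

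**What to change.** In SAP 13.5.7, analyse 3.7 and 3.11 with a repeated-measures model on the Week 18 and Week 76 changes. Include baseline, randomized treatment, visit and treatment-by-visit terms, with unstructured covariance and a named simpler structure as fallback for the small TART subset. Report the Week 76 mean change from baseline as the result.

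Keep the ANCOVA as a supportive analysis, labelled as using only subjects with Week 76 data, and give the number contributing to each analysis.

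Record the chosen model in Section 15 with a reason, since the treatment-by-visit term and the covariance structure also go beyond the protocol's wording.

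The cost is SAP wording and one additional model. No new data are needed, because both visits are already scheduled.

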#### **13.5.3.1 Statistical Modeling and Testing**

Statistical analysis will be achieved via an ANCOVA model. If non-Normality is evidenced via Normal scores plot and plots of predicted versus residual values, the analysis will be accompanied by a rank-based ANCOVA model. The change from baseline to study Week 18 (12 weeks of randomized treatment) on the log scale will be the dependent variable; randomized treatment group ( $0 = \text{placebo}$ ,  $50 = 50 \text{ mg QD tildacerfont}$ ,  $100 = 100 \text{ mg QD tildacerfont}$ , and  $200 = 200 \text{ mg QD tildacerfont}$ ) as a fixed effect; baseline TART Volume and the baseline GC dose (in HCe) as continuous covariates; the randomization stratum ( $A4 \leq 4 \times \text{ULN}$  versus  $A4 > 4 \times \text{ULN}$ ) as categorical explanatory variables. The estimation method for the ANCOVA model will REML. A significance level of 0.05 2-sided will be applied.

The ranked value is obtained by ranking all non-missing change from baseline values at the specified analysis visit, if a rank-based model is used.

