#### **Presentation of Analysis Results**

The log scale change from baseline (CFB) least squares (LS) means will be extracted from the model for each tildacerfont dose and placebo, along with the associated SEs and 95% CIs. Further, the treatment effect for each tildacerfont dose versus placebo, being the corresponding difference in log scale LS means, will also be extracted along with the associated SE, 95% CI and 2-sided p-values.

To facilitate ease of interpretation, the log scale CFB LS means for each tildacerfont dose and placebo and the difference between each tildacerfont dose and placebo in log scale CFB LS means (along with the associated 95% CI) will be back transformed as described for the Primary Efficacy Analysis.

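### Week 76 TART volume is sent to the SF-36 ANCOVA on untransformed change, while Week 18 TART volume is modelled as log change, and the SAP gives no reason for the difference

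*SAP*

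**What the plan says.** **Week 18 (endpoint 3.3).** SAP 13.5.3.1 specifies an ANCOVA: "The change from baseline to study Week 18 (12 weeks of randomized treatment) on the log scale will be the dependent variable". Covariates are baseline TART volume (untransformed) and baseline glucocorticoid dose, with treatment and randomization stratum as factors. There is no sex term. If non-normality is seen, "the analysis will be accompanied by a rank-based ANCOVA model". Under SAP 13.5.3.2 the least squares means and differences "will be back transformed as described for the Primary Efficacy Analysis", so they are read as ratios or percent changes.

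**Week 76 (endpoint 3.11).** SAP 13.5.7 says: "For Exploratory Efficacy Analyses 3.7 and 3.11, an ANCOVA model will be applied, and results described, in the same manner as that" for endpoint 3.6. It also says that Week 76 efficacy is judged against baseline. Protocol 9.4.1 likewise limits Week 76 efficacy analyses to change from baseline.

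**The SF-36 method (endpoint 3.6).** SAP 13.5.6.1 says that "the model will comprise the (rank of, if non-normal residuals) change from baseline value to study Week 18 as the dependent variable". SAP 9.3.11 defines change from baseline as an arithmetic difference. The model includes sex and baseline SF-36 total score. SAP 13.5.6.2 reports plain least squares means and differences, with no back-transformation.

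**Protocol.** Section 9.4.4.1 planned a repeated-measures mixed model for Week 76 TART volume. SAP Section 15 explains a change of model for acne and hirsutism only.

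**The concern.** Endpoints 3.3 and 3.11 are built on the same total lesion volume per man (SAP 9.3.21). The natural question is whether a change seen after 12 weeks continued to Week 76. With a ratio at one visit and a volume difference at the other, the modelled results do not line up.

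The cross-reference looks like a slip, because a method written for this measure stands in 13.5.3, while the one chosen brings in a quality-of-life score as covariate and a sex factor that has one level. If volumes are right-skewed, as the choice of log change at Week 18 suggests, the raw-scale estimate is weighted towards the largest lesions. At stake are the interpretability and precision of one exploratory endpoint.

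**Working it through.** The documents give no sample size, variance or power figure for TART, so there is no plan figure to reproduce. The sample size in protocol 9.2 concerns A4 and has no bearing here.

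**1. The two specifications side by side**

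| Item | Week 18 (3.3) | Week 76 (3.11, read through 3.6) |
|---|---|---|
| Outcome | log change | untransformed change, or its rank |
| Baseline covariate | TART volume | SF-36 total score, as written |
| Sex term | none | included; all subjects are male |
| Modelled result | back-transformed ratio | volume difference |
| Reason for the difference in SAP Section 15 | – | none |

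**2. What the raw scale weights.** Take assumed volumes 0.2, 0.5, 1, 2 and 10, each halving.
- Log change: log(0.5) = -0.693 for every lesion.
- Raw change: -0.1, -0.25, -0.5, -1.0, -5.0, which sums to -6.85.
- Share from the largest lesion: 5.0 / 6.85 = 73%.

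**3. What ranks can test.** SAP 13.5.6.1 ranks all non-missing changes. The mean of n ranks is (n + 1)/2 by construction; with 15 men it is 8 whether lesions shrink, grow or stay the same. A rank ANCOVA can compare randomized arms but cannot test overall change against baseline. For the question that 13.5.7 states, the only usable model estimate is the raw one.

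**4. Illustrative power.** All inputs are assumptions:
- 15 or 20 men with TART at baseline
- log-normal baseline volume, log-SD 1.0 to 1.5
- 30% geometric-mean shrinkage, log-SD of change 0.5
- two-sided alpha 0.05, test of overall change against baseline

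The raw test fits change = a + b × (baseline volume - mean baseline volume) and tests a = 0 on n - 2 degrees of freedom. The log test is a one-sample t-test on log(follow-up / baseline); adding baseline volume moves it by less than one percentage point.

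| | Raw, no baseline covariate | Raw, baseline-adjusted | Log |
|---|---|---|---|
| 15 men | 33% falling to 20% as skew rises | 51-54% | 72-73% |
| 20 men | 41% falling to 25% | about 55% | about 85% |

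Across repeated runs the outer ranges were about 51-57% for the adjusted raw test and about 72-87% for the log test. Relative loss: 1 - 54/73 = 26% to 1 - 51/72 = 29% with 15 men, and 1 - 55/85 = 35% with 20.

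Part of the gap arises because the scales estimate different things. A 30% geometric-mean shrinkage with log-SD 0.5 is an expected arithmetic ratio of 0.7 × exp(0.5²/2) = 0.7 × 1.133 = 0.793, a 21% reduction.

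**5. Sensitivity to one lesion.** In a four-arm ANCOVA with 3 to 5 men per arm (assumed baseline log-SD 1.2, log-SD of change 0.5, 40% reduction on one dose), dropping the largest lesion moved the dose-versus-placebo estimate by more than one standard error in 9-13% of trials on the raw scale, 1-4% on the log scale and 2-5% on ranks.

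**The case against.** **Descriptive results remain comparable.** A reader might infer that nobody could tell whether TARTs kept shrinking. The documents do not support that. SAP 13.5.6.2 asks for 11-point descriptives, SAP 9.1 defines that set to include the geometric mean and the geometric mean ratio with its interval, and 13.5.7 carries the reporting over to 3.11. SAP 13.5.3.2 already asks for raw and percent change at Week 18. Only the modelled estimates are in different units. This part of the objection stands.

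**The planned test is not a bare raw t-test.** A reader might infer that one large lesion decides the Week 76 result, or that most of the power is lost. The 20-41% figures in the no-covariate column would suggest so, but they omit the baseline covariate that the model carries, once baseline volume is substituted for SF-36. The SAP also says "Statistical testing will be performed using a (rank-based, if non-normal residuals) ANCOVA model". The loss is then about a quarter to a third, and single-lesion influence is a risk in a minority of trials. This stands too, with two limits: no criterion is given for judging residuals non-normal, and the rank ANCOVA does not answer the against-baseline question.

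**The wording faults are minor in effect.** A one-level sex factor is aliased and changes no estimate, and reading baseline TART volume for baseline SF-36 is the obvious intent. Agreed; they matter mainly as evidence that the cross-reference was not checked.

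**The log scale has its own problem.** Log of zero is undefined. The extension endpoint 4.4 in SAP Table 1 counts men without TART at end of treatment, so full resolution is foreseen. A reader might assume that a zero-volume rule already exists for Week 18; SAP 9.3.21 and 13.5.3 contain none. Raw and rank change handle zeros directly, so the choice of scale is partly a trade-off.

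**Conclusion.** The mismatch is real and follows from the text alone: log change with back-transformation at Week 18, untransformed change with plain mean differences at Week 76, and no reason in SAP Section 15. The rank fallback does not repair it for a comparison against baseline.

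The size is moderate. Under the assumed inputs, power is about 51-57% for the baseline-adjusted raw test against about 72-87% on the log scale. These figures are illustrative, because the number of men with TART, the skew and the effect are all assumed.

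The reach is limited. Endpoint 3.11 is exploratory, confined to men with TART at baseline and outside alpha control (SAP 10.5). No primary or secondary conclusion depends on it. The point is worth correcting because it is cheap and the sponsor has already chosen a method for this measure.

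**What to change.** In SAP 13.5.7, refer endpoint 3.11 to 13.5.3 in place of the SF-36 method: log change to Week 76 as outcome, baseline TART volume (untransformed, as in 13.5.3.1) as covariate, no sex term, and estimates back-transformed to percent change. If the difference in scale is intended, justify it in Section 15 instead.

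Add one pre-specified rule for zero follow-up volume and apply it at both Week 18 and Week 76. Record in Section 15 the departure from the protocol's mixed model for Week 76.

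The cost is one cross-reference plus a new rule, settled before the Week 76 data are frozen. The downside is that with few men the log result may depend on the constant chosen for zero volumes. Keep the raw or rank result as a supportive analysis for that reason, using the raw one for change against baseline.
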